11.3.5. Safety and Tolerance Analysis

All patients who received at least one dose of any of the study medications will be included in the safety analyses. Vemurafenib + Sorafenib dose administration data will be listed and any dose interruptions and dose reductions will be summarized.

The incidence of all AEs (regardless of causality) and all treatment-related AEs (those AEs thought to be suspected related to study drug) will be summarized by NCI CTCAE version 5.0 term and maximum grade. The incidence of SAEs and AEs that lead to discontinuation of study drug will also be summarized. Listings of patients who discontinue study drug due to an AE and patients with SAEs and deaths will be presented. Narratives will be provided for patients who experience an SAE.

11.4. Stopping Rules

The study can be stopped early based on the following criteria:

- Per PI or sponsor discretion
- If none of the first 7 evaluable patients have disease control (CR+ PR +SD at 16 weeks)

12. STUDY MANAGEMENT

12.1. Ethics

This study will be conducted in compliance with the protocol, Good Clinical Practice (GCP), Guidelines of the International Conference on Harmonization (ICH) of Technical Requirements for Registration of Pharmaceuticals for Human Use, and in full compliance with the World Medical Association Declaration of Helsinki and its most recent amendments.

12.2. Institutional Review Board (IRB) Approval

Before study initiation, this protocol and informed consent form will be submitted for review and approval to the IRBs charged with oversight for the clinical sites. In addition, any form of proposed advertising and advertising text for patient recruitment must be

reviewed and approved by (Sponsor) prior to submission to the IRB. The Investigator will forward to (Sponsor) -nominated designee a copy of the IRB's approval of this protocol, any amendments, informed consent form, and any modifications to the informed consent, based on the FDA regulations set forth in 21 CFR 56 of the Code of Federal Regulations, as well as those of the applicable regulatory bodies in all other participating countries outside of the U.S.

In addition, the Investigator will be responsible for forwarding to Sponsor nominated designee a description of the IRB board members (including profession and affiliation) or a United States (US) Department of Health and Human Services (DHHS) General Assurance number and expiration date. If neither of these is available, the chairperson must submit a statement indicating that the members of the board responsible for the review meet FDA and other appropriate regulatory requirements. In addition, the labeling for all approved study drugs should be submitted to the IRB for informational purposes.

12.3. Informed Consent

Written informed consent of the patient to participate in the study must be obtained and documented by the Investigator in accordance with the FDA regulations set forth in 21 CFR 50 as well as the applicable regulatory bodies in all other participating countries outside the United States.

The Investigator must provide the patient with a copy of the informed consent form in a language understandable to the patient. Written consent should be obtained before any protocol-required procedures are performed, including any procedure not part of normal patient care (e.g., withdrawal of current medications).

Changes made by a participating site to the recommended informed consent must be forwarded to HRI/Triligent for approval prior to submission to the corresponding IRB. A copy of the signed informed consent will be given to the patient or their legal representative and a copy must be retained in the Investigator's study records.

12.4. Trial Registration and Results Posting Requirements

Under the terms of the Food and Drug Administration Modernization Act (FDAMA) and the Food and Drug Administration Amendments Act (FDAAA), the Sponsor of the trial is solely responsible for determining whether the trial and its results are patient to the requirements for submission to the Clinical Trials Data Bank, <http://www.clinicaltrials.gov>. Information posted will allow patients to identify potentially appropriate trials for their disease conditions and pursue participation by calling a central contact number for further information on appropriate trial locations and trial site contact information.

12.5. Reporting to Regulatory Authorities, Ethics Committees and Investigators

HonorHealth will be responsible for the expedited reporting of safety reports originating from the Study to the Ethics Committees and Institutional Review Boards (IRB), where

applicable.

HonorHealth will be responsible for the distribution of safety information to its own investigators, where relevant, in accordance with local regulations.

12.6. Annual Reports and Study Close-Out

Any study report submitted to the IRB by the Sponsor-Investigator should be copied to Bayer and Genentech. This includes all IRB annual reports and the Clinical Study Report (final study report). Additionally, any literature articles that are a result of the study should be sent to Bayer and Genentech per the terms detailed in the contract.

12.7. Investigator Obligations

12.7.1. Form FDA 1572

The Investigator must provide a fully executed Form FDA 1572. Any additions to the study must be provided via a new fully executed Form FDA 1572. Others should follow FDA guidance “Information Sheet Guidance for Sponsors, Clinical Investigators, and IRBs”.

12.7.2. Curriculum Vitae

The Investigator must provide his/her current signed and dated curriculum vitae and a current signed and dated curriculum vitae for each sub-Investigator listed on Form FDA 1572. Current signed and dated curriculum vitae is defined as updated within 2 years of study start up.

12.7.3. Investigator Protocol Agreement

The Investigator must sign the Investigator’s Protocol Agreement. The original must be kept on file at the Investigator site and a copy provided to HRI. The completed Investigator’s Protocol Agreement signifies agreement to comply with all procedures outlined by this protocol by the Investigator. An Investigator’s Protocol Agreement must be signed if and when a protocol amendment is issued by (Sponsor/CRO).

12.7.4. Financial Disclosures

The Investigator and sub-Investigator(s) must complete a Clinical Investigator Financial Certification/Disclosure Statement to report financial interests and arrangements that may be of concern to FDA per 21 CFR 54.

12.7.5. Laboratory Certifications and Normal Ranges

The Investigator will indicate on the Form FDA 1572 the name and location of any local laboratories that will be used for laboratory assessments. The Investigator will provide a copy of all clinical laboratory certifications, certification numbers, and dates of certifications, and. Normal ranges for all laboratory tests will be included with all reported results. Updated versions of these documents must be provided to HRI appropriate. In the event the clinical laboratory is changed during the study HRI will be promptly notified,

and the Form FDA 1572 will be updated. Appropriate documentation will be submitted to HRI to verify the certification of the new laboratory.

All radiology facilities being utilized outside the investigative site must be pre-approved by HRI.

12.7.6. Confidentiality

The Investigator and any other study personnel involved in this study shall not disclose, or use for any purposes (other than for the performance of this study), any data, records, or other information (hereinafter collectively “information”) disclosed to the Investigator or other study personnel. Such information shall remain the confidential and proprietary property of HRI and shall be disclosed only to the Investigator or other designated study personnel.

The obligation of non-disclosure shall not apply to the following:

- Relevant disclosure to potential study participants for the purpose of obtaining informed consent;
- Information after such time that it is or becomes publicly available through no fault of the Investigator or other study personnel; and,
- Information after such time that it is disclosed to the Investigator by a third party entitled to disclose such information.
- If the study site is a ‘covered site’ under the definitions of the Health Insurance Portability and Accounting Act (HIPAA), the Investigator will ensure that the patient consents to the use of data by HRI/Bayer/Genentech and its designees for the purposes of regulatory submissions, study publications, and drug approval.

12.8. Source Documentation

Source documents serve as the evidence of the existence of the patient and the data collected for this trial. Source documents will be the responsibility of the Investigator and will be filed at the site and available as needed by the Sponsor or assigned clinical monitor.

Data captured on the eCRFs is to be transcribed from source document and must be consistent with any discrepancies explained and documented.

12.9. Case Report Forms

All the clinical data will be captured by the site on electronic case report forms (eCRFs). The eCRFs will be used for all consented patients. The investigator and trained trial personnel will enter and edit the data via a secure network, with secure identification and password requirement. A complete electronic audit trail will be maintained. The investigator will be required to provide approval of all data to confirm accuracy. Copies of the eCRFs will be provided to the investigator at the conclusion of the trial.

HRI will monitor the study to verify study data, medical records, and eCRFs in accordance with current ICH GCP guidelines as well as other applicable regulations and guidelines.

12.10. Data Management and Monitoring / Auditing

Data monitoring procedures will be carried out by an HRI appointed monitor and will be performed on a regular basis to comply with Good Clinical Practice guidelines.

Review of the case report forms, cross-reference with source documentation (including radiology review), review of study related regulatory documents and logs (e.g., enrollment, study site staff training and delegation) and review of drug infusion records will be monitored on an ongoing basis during monitoring sessions. The monitor will ensure that the investigation is conducted according to protocol design and regulatory requirements. At the conclusion of the monitoring visit, the site monitor will meet with the site staff to discuss and request specific corrections to the case report forms, and/or request clarification, and/or additional source documentation. The Principal Investigator and Clinical Research Coordinator responsible for the study will be provided with a follow-up letter for resolution of the findings.

The HRI monitor will complete a written monitoring report. The report will include a summary of what the site monitor reviewed and the site monitor's statements concerning the significant findings/facts, deviations and deficiencies, conclusions, actions taken or to be taken, and/or actions recommended to ensure compliance. The Principal Investigator will be expected to submit any Corrective Action Plans, in writing.

12.10.1. Data Safety and Monitoring

An independent Data Safety and Monitoring Committee (DSMC) will be formed to evaluate the safety and effectiveness of the study medication for each subject. The DSMC will also review all SAEs and AESIs reported by each site. The DSMC will review study data to determine if endpoints are being met and if the study can continue with or without changes to the protocol or if the study should be terminated immediately due to safety concerns or lack of data to support study endpoints. Findings and recommendations of the DSMC will be reported to the Sponsor after each meeting.

12.11. Record Retention

In accordance with applicable regulatory requirements, following closure of the study, the Investigator will maintain a copy of all site study records in a safe and secure location. HRI will inform the Investigator of the time period for retaining these records in order to comply with applicable regulatory requirements.

HRI reserves the right to terminate the study for refusal of the Investigator and/or investigational site to comply with any requirements stated in this study protocol.

Appendix A: Schedule of Events

Assessment	Screening Within 28 Days	Cycle 1					Cycle 2 +				Prior to Cycles 3, 5, 7, etc.	Off Treatment Visit ¹¹	Follow-up
		Day 1		Day 8	Day 15	Day 22	Day 1						
Window												14-28 (± 2 days) of last dose	30 days of last dose, then every 3 months
Signed informed consent	X												
Review inclusion/exclusion	X	X											
Medical history ¹	X												
Complete Physical Exam	X												
Direct Physical Exam		X ²		X ³	X	X	X ³					X	
Height (cm)	X												
Weight (kg)	X	X ²					X ³					X	
BSA calculation		X ²					X						
Vital signs ⁴	X	X ²		X ³	X	X	X ³					X	
ECOG PS	X	X ²		X ³	X	X	X ³					X	
CT/ MRI scan / tumor measurements ⁵	X										X		
ECG ⁶	X	X			X		X ⁶						
CBC w/differential & PLTs	X	X ²		X ³	X	X	X					X	
Serum chemistries ⁷	X	X ²		X ³	X	X	X					X	
PT/INR	X	X ^{2, 8}					X ⁸					X ⁸	
CA 19-9 (or CA 125, or CEA if not expressers of CA 19-9)	X										X	X	
Serum pregnancy	X	X ²					X					X	
Confirm KRAS, BRAF Mutation Status ¹³	X												
Blood for correlative analysis (3 X 10 mL)	X						X					X	
Optional Tumor Tissue ¹⁵	X	<-----X----->											
Concomitant medications ⁹	X	X		X	X	X	X					X	
Adverse events ¹⁰		X		X	X	X	X					X	
Contact Information Review	X	X										X	X
Telephone follow-up ¹²													X

Drug Accountability- (Section 9.4)		X					X					X	
TREATMENT													
Vemurafenib ¹⁴		X ----->					X ----->						
Sorafenib ¹⁴		X ----->					X ----->						

Schedule of Events footnotes:

1. To include concurrent baseline conditions (using NCI CTCAE, version 5.0), prior cancer therapy (including documentation of prior surgery, adjuvant or neoadjuvant chemotherapy and radiotherapy).
2. Should be performed < 24 hours prior to the initiating study treatment day on C1/D1.
3. Should be performed within 72 hours prior to treatment on day 1 of each cycle beyond cycle 1.
4. Vitals signed include blood pressure, pulse, respiratory rate and temperature.
5. Computed tomography (CT) / magnetic resonance imaging (MRI) scan to document disease status (including chest, abdomen, pelvis, and other regions as clinically indicated. In addition, a brain scan is required to exclude brain metastases if clinically indicated only. If a CT scan was taken within 28 days prior to first dose, a new scan is not necessary. (see RECIST 1.1 criteria in Section 7.1). Follow-up scans are due every 2 cycles (prior to cycle 3, 5, 7, etc.)
6. ECG (Cycles 1 through 3, then every 3 cycles 6, 9, 12 etc.)
7. To include glucose, creatinine, BUN, total bilirubin, AST, ALT, alkaline phosphatase albumin, LDH, total protein, and electrolytes (sodium, potassium, phosphorus, chloride, CO₂, magnesium, calcium). In patients with known Gilbert's syndrome, it is recommended to perform a direct bilirubin and indirect bilirubin. Calculate creatinine clearance (Cockcroft-Gault equation)
8. PT/INR required only for patients on warfarin.
9. To include all medications and supplements taken within 30 days prior to study enrollment. The use of grapefruit juice and St. John's Wort (hyperforin) is prohibited during study treatment. The treating investigator is to discuss this with the patient prior to initiating study treatment and will review list of all medications and supplements during the course of the study.
10. Patient will be followed until resolution of any drug-related AE or SAE occurring during the study, including, within 30 days of last administration of study medication, or when the patient begins alternative therapy; whichever is sooner.
11. Off Treatment -Early Termination assessments can be completed 14-28 (+/- 2) days from the last dose of study treatment.
12. Follow-up assessments for survival in person or by telephone will be conducted in all patients 30 days after the last dose of study treatment and then every 3 months until study completion (may be done through medical record review or follow up phone calls). Receipt of second line therapy will be recorded.
13. Confirm KRAS and BRAF mutation status. For those patients in which the mutation status of KRAS and BRAF kinases has not previously been determined, the patient must have an archival tumor specimen (primary or metastatic site) available to submit to confirm KRAS and BRAF status. The results of the mutation status are required for determining patients eligibility for this trial
14. Patients will be asked to take the specified number of tablets for their prescribed dose on an empty stomach at a regular time each day with water. Doses should be taken either one hour prior or two hours after a meal. Approximately 12 hours should elapse between doses.
15. For those patients that consent to the optional tissue collection for RPPA analysis, tissue will be collected from a newly obtained core or excisional biopsy of a tumor lesion if performed recently (within 30 days prior to study treatment on Day 1) and during their participation in the study should they be scheduled for a biopsy as part of their routine care during their participation in the study through the follow-up period

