6.3.3. Tumor Assessments Every 2 Cycles (Every 8 Weeks)

- Tumor measurements per RECIST 1.1 (before C3, C5, C7 etc.). Tumor measurements may be obtained at the discretion of the principal investigator if clinically indicated.
- CA19-9 (or CA 125, or CEA if not expressers of CA 19-9) before C3, C5, C7 etc.)

In order to more precisely determine time to progression, the investigator is encouraged to obtain radiological assessments earlier if there is a strong clinical suspicion of disease progression, in order to either confirm or refute the clinical impression.

Reassessment of the extent of tumor should be made by the same imaging methods used to establish baseline tumor measurements.

6.4. Off Treatment Visit – to be Completed 14-28 (+/-2) Days From the Last Dose of Study Treatment

- Directed physical exam, if deemed necessary
- Weight (kg)
- Vital signs (blood pressure, pulse, respiratory rate, and temperature)

- ECOG Performance status
- Hematology: CBC with differential and platelet count
- Serum chemistries: glucose, creatinine, BUN, total bilirubin, AST, ALT, alkaline phosphatase albumin, LDH, total protein, and electrolytes (sodium, potassium, phosphorus, chloride, CO₂, magnesium, calcium). In patients with known Gilbert's syndrome, it is recommended to perform a direct bilirubin and indirect bilirubin. Calculate creatinine clearance (Cockcroft-Gault equation).
- Coagulation: PT, INR– only required for patients on warfarin
- CA19-9 (or CA 125, or CEA if not expressers of CA 19-9)
- Serum pregnancy if applicable
- Blood for correlative analysis- 3 X 10 mL
- AEs using the NCI CTCAE 5.0
- Concomitant medication notation
- Complete Drug Accountability (Per Section 9.4): Collect all previously distributed study medications and review the completed Patient Study Drug Diary with the patient and address any discrepancies with the patient.
- Confirm contact information for patient and a designated family member, and primary care physician and remind patient of follow-up telephone contact that will be conducted 30 days after the last dose of study treatment and then every 3 months for survival status.

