6.5. Follow-up Procedures

Patients will be followed for 30 days after completion of (or early withdrawal from) study treatment for adverse events.

Patients will be followed for survival end points every 3 months until study completion (may be done through medical record review or follow up phone calls). Receipt of second line therapy will be recorded.

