8.3. Adverse Event Reporting

The study period during which AEs and SAEs as described in Section 8.2 where the patient has been exposed to study treatment must be reported. Reporting period begins at the time of initiation of study treatment and ends 30 days following the last administration of study treatment or study discontinuation/termination, whichever is earlier. After this period, investigators should only report SAEs that are attributed to prior study treatment.

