8.11.2. Follow-up Information

Each serious adverse event must be followed up until resolution or stabilization, by submission of updated reports. Additional information may be added to a previously submitted report by any of the following methods:

- Adding to the original MedWatch 3500A report and submitting it as follow-up
- Adding supplemental summary information and submitting it as follow-up with the original MedWatch 3500A form
- Summarizing new information and faxing it with a cover letter including patient identifiers (i.e. D.O.B. initial, patient number), protocol description and number, if assigned, brief adverse event description, and notation that additional or follow-up information is being submitted (The patient identifiers are important so that the new information is added to the correct initial report)

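### The schedule leaves up to 18 of the 30 days of post-treatment adverse event follow-up without a planned check, and the rules for ending follow-up conflict, most sharply for open drug-related SAEs

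*Combined protocol and SAP*

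**What the plan says.** The body text sets a 30-day obligation. Section 6.5 reads: "Patients will be followed for 30 days after completion of (or early withdrawal from) study treatment for adverse events". Sections 5.3 and 5.7 say the same in substance, and none of the three makes an exception for a patient who moves to another therapy.

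The visit plan is different. The heading of Section 6.4 gives the off-treatment visit as "to be Completed 14-28 (+/-2) Days From the Last Dose of Study Treatment", and the Appendix A column header repeats the window as "14-28 (± 2 days) of last dose". The AE row of Appendix A is marked at that visit and is blank in the Follow-up column. Footnote 12 describes the contact at Day 30 this way: "Follow-up assessments for survival in person or by telephone will be conducted in all patients 30 days after the last dose of study treatment". Section 6.4 likewise presents it as a telephone contact for survival status.

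Two further rules govern when AE work ends:

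- **Open events.** Footnote 10 of Appendix A says drug-related AEs and SAEs are followed to resolution, then adds "within 30 days of last administration of study medication, or when the patient begins alternative therapy; whichever is sooner". Section 8.11.2 says: "Each serious adverse event must be followed up until resolution or stabilization, by submission of updated reports".
- **Reporting period.** Section 8.3 ends it 30 days after the last administration "or study discontinuation/termination, whichever is earlier", and Section 8.10 repeats this. After that, Section 8.3 keeps SAEs attributed to study treatment reportable, and Section 8.10 adds all deaths regardless of cause.

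**The concern.** Safety is the first secondary objective, and Section 11.3.5 summarizes AE incidence by term and maximum grade, with SAE listings and narratives. Those summaries assume one window applied to every patient. As written, staff working from the schedule would stop asking about AEs at the off-treatment visit, while staff working from Section 5.7 or 6.5 would go on to Day 30.

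Footnote 10 matters most for patients who leave treatment with unresolved toxicity and start something else. Following the footnote, the outcome of an open drug-related SAE would be left unrecorded; following Section 8.11.2, it would be pursued. Toxicity is not hypothetical here: Section 1.4 reports dose holds among the first three patients to complete a cycle, for two instances of grade 3 rash and one of grade 3 hypertension.

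**Working it through.** The plan gives no figure to reproduce. The check is day arithmetic on the stated windows and a side-by-side reading of the rules. Days are counted from the last dose.

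**1. Days without a scheduled AE check**

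Inputs: visit window 14 to 28 days, plus or minus 2 (Section 6.4; Appendix A header and footnote 11); AE follow-up of 30 days (Sections 5.3, 5.7, 6.5); no AE mark after the off-treatment visit (Appendix A).

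- Earliest visit: 14 − 2 = Day 12. Latest visit: 28 + 2 = Day 30.
- Uncovered days = 30 − visit day.

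| Off-treatment visit | Uncovered days | Share of 30 days |
|---|---|---|
| Day 12 | 30 − 12 = 18 | 60% |
| Day 14 | 30 − 14 = 16 | 53% |
| Day 28 | 30 − 28 = 2 | 7% |
| Day 30 | 30 − 30 = 0 | 0% |

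Section 5.3 cites Section 6.4 for the 30-day AE follow-up, but Section 6.4 is the off-treatment visit itself and assigns the later contact to survival. No other section assigns AE questions to the Day 30 contact.

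**2. End of follow-up for an open event**

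| Source | Events covered | End point |
|---|---|---|
| Section 8.11.2 | Every SAE | Resolution or stabilization |
| Appendix A, footnote 10 | Drug-related AEs and SAEs | Sooner of its listed events, one being new therapy |

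The two overlap on drug-related SAEs. Footnote 10 is awkwardly worded: its 30 days may cap follow-up, or may describe when the event occurred. On either reading the start of new therapy ends follow-up, so an unresolved drug-related SAE falls under two incompatible instructions.

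**3. End of the reporting period**

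Sections 5.7 and 6.5 give 30 days, and Section 6.5 keeps that after early withdrawal from treatment. Sections 8.3 and 8.10 give the earlier of Day 30 and study discontinuation or termination. If that clause is applied when a patient leaves the study, or when the study stops, the period closes before Day 30. Taking out what stays reportable afterwards (treatment-attributed SAEs and all deaths) leaves non-serious AEs and non-fatal SAEs not attributed to treatment.

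**4. Scale**

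Section 11.2 plans 12 evaluable patients at full accrual and up to 24 enrolled. If one patient's only occurrence of an AE term is missed, the incidence of that term shifts by 1/24 = 4.2 percentage points with 24 treated, or 1/12 = 8.3 with 12. This is an illustration; the number of events that would be missed cannot be derived from the documents.

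**The case against.** The best defence is that the obligation is already there. Three sections require 30 days, Section 8.4 accepts AEs however they come to light, and a Day 30 call is already planned. On that view only a mark in a table is missing. This stands as far as it goes: the gap is in scheduled checks, not in the stated duty. It does not answer footnote 10, where two explicit instructions conflict.

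Several stronger readings are tempting, and the documents do not support them.

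- **That most of the 30 days goes unchecked.** The 60% is the extreme of a range that reaches zero.
- **That footnote 10 shortens AE collection, for example by 16 days if new therapy starts at Day 14.** The footnote governs how long existing drug-related events are followed. The period for reporting new events is set in Section 8.3, which does not name new therapy as an end. Nor do the documents say when next therapy starts; the 2-week washout in the exclusion criteria concerns entry to this trial.
- **That the Day 30 contact may be a chart review.** In Sections 5.7 and 6.5 that option is attached to the 3-monthly survival follow-up, and Section 6.4 calls Day 30 a telephone contact. Footnote 12 is at most ambiguous.
- **That a futility stop ends all AE reporting at once.** This is one reading of loose wording. Sections 5.8 and 6.6 send discontinued patients to the end-of-treatment visit and follow-up, Section 6.6 separates stopping treatment from withdrawing consent, and attributed SAEs and deaths remain reportable on any reading.
- **That every AE must be followed to resolution.** Section 8.11.2 covers SAEs only. Ending follow-up of non-serious drug-related AEs at new therapy is a choice the sponsor may make.

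**Conclusion.** The point holds in three limited parts. First, 0 to 18 of the 30 days have no scheduled AE check, depending on the date of the off-treatment visit; this assumes the visit can be held anywhere in its stated window and that the Day 30 contact is run as described, for survival. Second, footnote 10 and Section 8.11.2 contradict each other for a drug-related SAE still open when new therapy begins; this needs no assumption. Third, the end-of-period clause in Sections 8.3 and 8.10 is ambiguous against Section 6.5, with the possible loss confined to non-serious AEs and non-fatal SAEs not attributed to treatment. The primary endpoint is unaffected. The change should be made: it concerns a stated secondary objective, the rules conflict as written, and the remedy is cheap.

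**What to change.** 1. In Appendix A, mark the AE row at the existing Day 30 contact, and state in Section 6.4, Section 6.5 and footnote 12 that this contact asks about AEs as well as survival. Correct the cross-reference in Section 5.3 to match.
2. Amend footnote 10 so that SAEs follow Section 8.11.2 whether or not new therapy has started. Record the start date of new therapy; receipt of later therapy is already captured. The sponsor should choose the end point for non-serious drug-related AEs and state it once.
3. Reconcile the end-of-period wording in Sections 8.3 and 8.10 with Sections 5.7 and 6.5, so that it is clear what happens after early withdrawal and after study termination.

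The cost is amendment wording, a few questions at a call already planned, and continued SAE follow-up for some patients on new therapy. Some events arising after new therapy will be harder to attribute; the recorded start date helps with that but does not remove it.
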